1. SYNOPSIS

PROTOCOL NUMBER:	RIG01
INVESTIGATIONAL MEDICINAL PRODUCT (IMP):	BPL Human rabies immune globulin (HRIG)
TITLE:	A Prospective, Randomized, Blinded, Parallel-group, Non-inferiority Phase II/III Study of the Safety and Effectiveness of BPL HRIG With Co-administration of Active Rabies Vaccine in Healthy Subjects
PHASE:	II/III
OBJECTIVES:	
1. To demonstrate non-inferiority of BPL HRIG compared to an FDA-licensed HRIG product, in terms of the proportion of subjects achieving anti-rabies antibody titer of ≥ 0.5 IU/mL at Day 14 following treatment with HRIG in conjunction with active rabies vaccine.2. To compare the PK of BPL HRIG in conjunction with active rabies vaccine, with FDA-licensed HRIG product in conjunction with active rabies vaccine.3. To assess whether BPL HRIG interferes with the development of the host-immune response when given simultaneously with active rabies vaccine, relative to an FDA-licensed HRIG product.4. To evaluate the safety and tolerability of BPL HRIG in comparison with FDA licensed HRIG product.
STUDY DESIGN:	
This will be a prospective, randomized, blinded, parallel-group, non-inferiority, phase II/III study of the pharmacokinetics and safety (and tolerability) of simulated post-exposure prophylaxis with BPL HRIG with co-administration of active rabies vaccine in healthy subjects.
 
Screening visit (within 28 days prior to baseline) Screening evaluations will include viral serology, biochemistry, hematology and other tests to assess eligibility.
 
Baseline (Day 0) Eligible subjects will be randomly assigned to one of two treatment groups:

- Treatment A: BPL HRIG + active rabies vaccine
- Treatment B: Comparator HRIG + active rabies vaccine

Pre-dose samples will be collected for anti-rabies antibody serum titer, markers of hemolysis, and long-term archiving. Subjects will then be administered their randomized treatment for Day 0.

On-Study (Days 0-140)

Pharmacokinetic assessments of anti-rabies antibody serum titer will be conducted at the following time points: days 3, 5, 7, 14, 28 (4 weeks), 49 (7 weeks) and 140 (20 weeks).

Additional doses of active rabies vaccine (will be administered, after the collection of the blood sample for anti-rabies antibody serum titer, on days 3, 7, 14, and 28.

Adverse events will be monitored from the screening visit and throughout the study.

End-of-Study Assessment (Day 140)

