7.4.1. Before Dosing

The following assessments will be performed at all visits:

- Check for any new or changed adverse events and concomitant medications since the last visit
- Oral temperature. If the participant is febrile (oral temperature $>38.0^{\circ}\text{C}$ (100.4°F) or has an acute illness, active rabies vaccine must not be given. The subject may continue in the study but should receive no further doses of active rabies vaccine and will not be eligible for the per protocol population.

- Injection site assessment (only if symptoms were observed at the previous visit)
- Blood samples will be taken for rabies virus neutralizing antibodies (see [Section 8.1.4](#))

Reserve blood samples will be taken (see [Section 7.9.1](#))

In addition, the following assessments will be performed at the specified visits (see also the Schedule of Assessments in [Appendix G](#)):

- Vital signs: sitting blood pressure (mmHg) after a 5-min rest, pulse rate and respiration rate – Day 28 (see [Section 8.2.8](#))
- Blood samples will be collected for the following assessments:
 - markers of hemolysis (DCT, LDH, plasma free hemoglobin, serum haptoglobin and serum bilirubin) on Day 3. These tests including CBC may be repeated on Day 5, Day 7 and Day 14 depending on results obtained at the previous visit (see [Section 8.2.7](#)).
- A urine sample for hemosiderin – Day 3. This test may be repeated on Day 5, 7 and Day 14 depending on results obtained at the previous visit (see [Section 8.2.7](#)).

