5. SCHEDULE OF ASSESSMENTS

Each subject will undergo a total of 8 visits. Subjects' eligibility will be assessed at Screening, which can occur up to 28 days prior to dosing. Following a repeat eligibility check at Day 0, eligible subjects will be randomized and dosed with the randomized treatment (HRIG/vaccine or Comparator HRIG/vaccine on Day 0. Further administration of rabies vaccine, PK sampling and safety assessments will be conducted on Days 3, 5 (PK sampling only), 7, 14 and 28. An additional visit for PK sampling and safety assessment will take place on Day 49 (7 weeks) and Day 140 (20 weeks). The last visit will be the End-of-Study Assessment which will take place on Day 140 (20 weeks). This visit will comprise the final PK sample and safety assessments. The end of the trial is

defined as the last subject’s last End-of-Study Assessment (or the date of their last data collected, if the subject has an AE at the End-of-Study Assessment that needs to be followed).

Visit Number	1	2			3	4	5	6	7	8	9
Visit Assessment	Screening	Baseline									End-of-Study Assessment
Visit Timing	up to Day -28	Day 0			Day 3	Day 5	Day 7	Day 14	Day 28 (±2 days)	Day 49 (±4 days)	Day 140 (±7 days)
		pre-dose	dosing	30 min post-dose							
Informed Consent ^a	X										
Demography/Medical History	X										
Eligibility	X	X									
Physical Examination	X									X	X
Height	X										
Weight	X	X ^b									X
ECG	X										X
Vital Signs	X	X							X	X	X
Body Temperature (oral)		X			X		X	X	X		
Pregnancy Test ^c	X	X									X
Hematology, Serum Biochemistry, Urinalysis	X										X
Virology: HBsAg, HCV, HIV	X										X
Markers of Hemolysis: Direct Coomb’s Test, LDH, Plasma Free Hemoglobin, Serum Haptoglobin, Serum bilirubin, Urine Hemosiderin		X			X ^{d,k}	X ^{d,k}	X ^{d,k}	X ^{e,k}			
Archive Serum Sample*		X									X
Randomization ^f		X									
Administration of BPL HRIG / Competitor HRIG			X								
Administration of Active Rabies Vaccine			X		X		X	X	X		
Rabies Virus Neutralizing Antibody		X			X ^e	X ^f	X ^e	X ^e	X ^e	X	X
Reserve Sample Collection ^h	X	X			X	X	X	X	X	X	X
Adverse Events	X	X	X	X	X	X	X	X	X	X	X
Injection Site Observations ⁱ		X		X							
Concomitant Medications	X	X			X	X	X	X	X	X	X

^a informed consent prior to screening procedures
^b for re-assessment of eligibility and calculation of volume to be administered
^c females of childbearing potential only: serum at screening and End-of-Study Assessment, urine dipstick pre-dose on Day 0

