7. GENERAL ANALYSIS CONVENTIONS

All tables, figures and listings will be produced using SAS (v9.4 or a more recent version).

Unless otherwise stated, categorical data will be presented using counts and percentages, whilst continuous variables will be presented using the mean, 95% confidence interval for the mean, standard deviation (SD), median, minimum, maximum, number of subjects (n) and number of missing subjects or data points. Minima and maxima will be quoted to the number of decimal places as recorded in the CRF; means, SDs and medians will be quoted to one further decimal place. Percentages will be rounded to one decimal place.

Subjects who withdraw from the analysis will have their data analyzed to the point of withdrawal. Subjects who complete all required assessments up to and including Day 14 will be eligible for the primary PK population. Other subjects who withdraw from the study will be eligible for the ITT population. Unblinded subjects will continue in study after being unblinded unless noted otherwise.

For the purpose of the statistical analyses visit labels may be used interchangeably as Visit and Day as in the table below regardless of actual timing of study visit. Sensitivity analyses will be performed to address any potential visit timing issues.

Visit Label	Visit 1	Visit 2	Visit 3	Visit 4	Visit 5	Visit 6	Visit 7	Visit 8	Visit 9
Intended Day	Day -28	Baseline, Day 0	Day 3	Day 5	Day 7	Day 14	Day 28	Day 49	Day 140

a. DEFINITION OF STATISTICAL SIGNIFICANCE

- Primary Efficacy Endpoint

The BPL HRIG treatment effect will be considered non-inferior to the active comparator HRIG treatment when the resultant p-value from the one-sided Farrington-Manning

Score Test for proportion difference is [REDACTED].

- Secondary Efficacy Endpoints

The secondary efficacy endpoint analyses will be considered statistically significant using a two-sided significance level of 0.05.

b. ANALYTIC POPULATIONS

The following analysis populations will be defined for this study.

- Intent-to-Treat [ITT] Population

The intent-to-treat (ITT) population will include all randomized subjects. All analyses will be performed using the ITT population.

- Safety Population

The safety population will be defined as all subjects who receive at least one dose of BPL HRIG / comparator HRIG. Safety data will be analyzed up to the point of withdrawal for applicable subjects. The safety population will be used for all safety analyses.

- Per Protocol [PP] Population

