The per protocol population will be split into the **primary** and **secondary** PK populations.

The **primary PK population** will be defined as all subjects who receive the full dose of BPL HRIG / comparator HRIG and the first 3 doses of active rabies vaccine on Visits 2, 3, and 5, and for whom the PK sample at Visit 6 is taken. This population will be used for the primary PK analysis and selected secondary PK analyses. The **secondary PK population** will be defined as all subjects who receive the full dose of BPL HRIG / comparator HRIG and all 5 doses of active rabies vaccine and for whom all required PK samples are taken. This population will be used for selected secondary PK analysis and the exploratory analysis.

Subjects with a pre-dose RVNA of \geq the LLOQ will be excluded from the all

analyses.

[REDACTED]

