[REDACTED] will be performing the RFFIT test and providing the results for data analysis. Subject serum will be tested in duplicates. If either individual test in duplicated set 1 fails QC, a second duplicate set of RFFIT tests will be run. The arithmetic mean value of the appropriate duplicate set, (set 1 if QC passed, set 2 if QC failed), will be used for the final reported rabies antibody titer [IU] for primary endpoint derivation. If the final arithmetic mean value is ≥ 0.5 IU/mL that subject-specific time point will be coded as 1 (success); otherwise if the final arithmetic mean value is < 0.5 IU/ml the time point will be coded as 0 (failure). If both duplicate sets fail the QC test,

the subject data is deemed non-evaluable. The proportion of subjects with RVNA titer ≥ 0.5 IU/mL is calculated as follows:

$$\frac{\sum(\text{successes}, 1)}{\sum(\text{all evaluable subject } i, n)}$$

Sensitivity analyses will be performed to assess impact of missing data, see section 8j.

f. SECONDARY EFFICACY ANALYSES

Secondary efficacy analyses 2 and 5 will be based on the secondary PK population. Secondary efficacy analyses 1, 3, and 4 will be based on the primary PK population, since timepoints post-Visit 6 are not included in these analyses.

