The second secondary analyses will be performed using an appropriate mixed model repeated measures [MMRM] analysis to assess for differences of the slope and the change in GMT of the titers at the days described below. The correlation structure involves multiple pieces, including measurement errors, random variation, and inter-individual variability. For the longitudinal data analysis, an unstructured correlation matrix for within-subject error will be assumed. Other correlation structures, including compound symmetry, will be examined as needed. The validity of this model will be assessed via standard modeling diagnostics and goodness-of-fit measures. Comparisons of geometric mean titers [GMTs] between the treatment group at each timepoint and across all timepoints will be reported. The final output will include one row indicating the mean change [95% confidence intervals] in titer across all PK assessments from Visit 2 [baseline] through Visit 7 by treatment group and one row for every specific timepoint thereafter. Additionally, the difference in the means [or the ratio of the GMT] between treatment groups, the corresponding 95% confidence intervals, associated chi-square test statistic, and p-value will be reported. A p-value of <0.05 will signal a statistically significant difference in titers. See table below for example output:

Parameter	Treatment Group Ns			Mean Change From Baseline (95% Confidence Intervals)		BPL HRIG + Vaccine versus Comparator HRIG + Vaccine		
	N _{BPL}	N _{CP}	N _T	BPL HRIG + Vaccine	Comparator HRIG + Vaccine	Difference in Means (95% CI)	Chi-Square	P-Value
Through Day 28	x	x	x	x.xx (x.xx, x.xx)	x.xx (x.xx, x.xx)	x.xx (x.xx, x.xx)	x.xx	0.xxx
Day 3	x	x	x	x.xx (x.xx, x.xx)	x.xx (x.xx, x.xx)	x.xx (x.xx, x.xx)	x.xx	0.xxx
Day 5	x	x	x	x.xx (x.xx, x.xx)	x.xx (x.xx, x.xx)	x.xx (x.xx, x.xx)	x.xx	0.xxx
Day 7	x	x	x	x.xx (x.xx, x.xx)	x.xx (x.xx, x.xx)	x.xx (x.xx, x.xx)	x.xx	0.xxx
Day 14	x	x	x	x.xx (x.xx, x.xx)	x.xx (x.xx, x.xx)	x.xx (x.xx, x.xx)	x.xx	0.xxx
Day 28	x	x	x	x.xx (x.xx, x.xx)	x.xx (x.xx, x.xx)	x.xx (x.xx, x.xx)	x.xx	0.xxx

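### The geometric mean titer model ends at Day 28 but is restricted to subjects who meet conditions arising after the Day 28 titer, so usable titers are discarded

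*SAP*

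**What the plan says.** - **Population for analysis 2.** SAP 8.f, with the same sentence in Protocol 10.5.3: "Secondary efficacy analyses 2 and 5 will be based on the secondary PK population".
- **Definition of that population.** SAP 7.b and Protocol 10.4 require the full HRIG dose and "all 5 doses of active rabies vaccine and for whom all required PK samples are taken". Neither document lists which samples are required.
- **Model.** Analysis 2 is "performed using an appropriate mixed model repeated measures [MMRM] analysis". Its overall row reports the mean change "in titer across all PK assessments from Visit 2 [baseline] through Visit 7 by treatment group", and the last row of the example table is Day 28.
- **Order of sample and dose.** The Protocol synopsis schedules the later vaccine doses "after the collection of the blood sample for anti-rabies antibody serum titer, on days 3, 7, 14, and 28". Footnote g of the flow chart agrees. Dose 5 therefore follows the Day 28 titer.
- **Later samples.** Days 49 and 140 are PK visits outside the model.
- **A route out of the population.** For a subject who is febrile or acutely ill at a vaccine visit, Protocol 7.4.1 says: "The subject may continue in the study but should receive no further doses of active rabies vaccine".
- **Competing statements.** SAP 7.b says: "All analyses will be performed using the ITT population". SAP 7 and Protocol 10.3 say that withdrawn subjects contribute data up to withdrawal. SAP 8.k rules out imputation and works from valid cases.

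**The concern.** A subject can give every titer that the model uses and still be removed because of something that happens later. Not receiving dose 5 is enough. On the natural reading of the sample condition, so is missing only Day 49 or Day 140. In each case all five post-baseline titers (Days 3, 5, 7, 14 and 28) are lost.

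Two things are at stake. The first is precision. A mixed model for repeated measures uses partial profiles under a missing-at-random assumption, and a complete-sample entry rule removes that advantage. Analysis 2 is a formal test of difference at two-sided 0.05, so lost precision makes a finding of no significant difference easier to reach.

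The second is selection. Fever, adverse events and withdrawal occur after treatment. If they relate to titer and differ between arms, the GMT ratio shifts. The best-case and worst-case analyses in SAP 8.i cover only the primary analysis, so nothing in the plan would reveal such a shift here.

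**Working it through.** **1. The plan's own figures.** No sample size or power is stated for analysis 2. The Protocol's 73 per group (Section 10.9) belongs to the Day 14 primary endpoint. It reproduces with the Farrington-Manning formula at 98% in both arms, margin 10%, one-sided 0.025 and 85% power (72.4, rounded up to 73), but it says nothing about the GMT model. The relevant planned figure is the loss: 162 × 0.90 = 145.8, about 146, so 16 subjects are incomplete.

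**2. Timing of the entry conditions against the last modeled titer.**

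| Condition | When | Relation to the Day 28 titer |
|---|---|---|
| Full HRIG dose, vaccine doses 1-3 | Days 0, 3, 7 | before |
| Vaccine dose 4 | Day 14 | before it, but after the Day 3-14 titers |
| Vaccine dose 5 | Day 28, after sampling | after |
| Day 49 and Day 140 samples (natural reading) | Days 49, 140 | after |

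The dose 5 condition is explicit. The last row is an inference.

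**3. Upper bound at the planned loss.** Suppose all 16 incomplete subjects have full Day 3-28 data. Titers discarded: 16 × 5 = 80 of 162 × 5 = 810, or 9.9%. Ratio of complete-case to all-data standard error: √(162/146) = 1.053. For other assumed shares of incomplete subjects:
- 5% (154 kept): 1.026
- 20% (130 kept): 1.116
- 30% (113 kept): 1.197

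These are upper bounds, because a subject who leaves before Day 28 has fewer titers to recover.

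**4. Missed samples, assumed independent with probability q each.** There are seven post-dose samples. The complete-case share is (1−q)^7 and the available share at one visit is (1−q), so the standard error ratio is √[(1−q)/(1−q)^7] = (1−q)^−3.
- q = 1%: share 93.2%, ratio 1.031
- q = 2%: share 86.8%, ratio 1.063
- q = 3%: share 80.8%, ratio 1.096

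If only the five samples through Day 28 are required, the ratio is (1−q)^−2: 1.041 at 2% and 1.063 at 3%. If the replacement set is the primary PK population, which itself needs the Day 14 sample, the ratio for days other than Day 14 is √[(1−q)²/(1−q)^7] = (1−q)^−2.5: 1.052 at 2% and 1.079 at 3%.

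**5. Size of a selection effect (illustration).** Let completion depend on log titer, with a log-odds of 0.25 to 1.0 per SD. The within-arm mean log titer then shifts by 0.03 to 0.09 SD at 90% completion, and by 0.05 to 0.17 SD at 80%. An equal shift in both arms cancels in the GMT ratio.

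**The case against.** **The ITT sentence may already cure this.** Read with the valid-case rule, it could mean that analysis 2 is also run on all randomized subjects with available titers. But SAP 8.f names a different population for this analysis, and a specific rule normally governs a general one. The documents do not reconcile the two, so this supports clarification rather than dismissal.

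**Day 140 is not stated.** This stands. A reader might take the definition as expressly demanding every sample to Day 140, but it names no visit, and the separate N columns for each row of the example table fit poorly with a fixed complete-case set. Shared use with analysis 5, which runs to Visit 9, makes Day 140 the natural reading. On the narrower reading, dose 5 still follows the last modeled titer.

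**A per-protocol set is legitimate.** It is. Requiring dose 4 is an ordinary condition for the Day 28 titer. That does not justify conditions that cannot affect any modeled titer. The stated reason for the split, that analyses 1, 3 and 4 have no timepoints after Visit 6, does not explain why a model ending at Visit 7 needs later events.

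**The size could be read as larger.** A reader might apply the 13-19% loss from step 4 to the 146 evaluable subjects and arrive at 127 to 118. That counts loss twice, because 146 is already net of 10%. Withdrawals also cluster missed visits in the same subjects, so independence is itself only an assumption.

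**Early titers are covered elsewhere.** This largely stands. Analyses 1, 3 and 4 use the primary PK population, and titers are summarized by arm at each timepoint.

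**Conclusion.** The entry rule for analysis 2 conditions on at least one event after the last modeled titer (dose 5), and probably on two more (the Day 49 and Day 140 samples). It discards titers that the model could use and conflicts with other statements in the plan. The effect is moderate: at most about 5% in the standard error at the planned 10% loss, and about 6-10% relative to an available-case model if each sample is missed independently with probability 2-3%. Those miss rates are assumptions; at 1% the figure is about 3%.

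A reader might infer that the GMT ratio is biased. The documents do not show this. Both arms follow the same vaccine schedule, HRIG is given once, and subjects and assessors are blinded. Fever is listed for both HRIG products as a class effect and for the vaccine, so selection that differs by arm is possible but not demonstrated. Nor does the point extend to analysis 5 in the same form: that analysis is descriptive, uses no mixed model and itself runs to Day 140. The primary conclusion is unaffected.

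**What to change.** - Run analysis 2 on the primary PK population, keeping the stated exclusion for pre-dose RVNA at or above the LLOQ. Use every available titer through Day 28. To keep the per-protocol question, use only titers taken before any missed vaccine dose: a subject without dose 4 contributes through Day 14, and one without dose 5 through Day 28. State the missing-at-random assumption.
- Keep the secondary PK population as a sensitivity analysis.
- Leave analysis 5 descriptive and summarize it on available cases.
- Define the required PK samples by visit in SAP 7.b and Protocol 10.4.
- Reconcile the ITT sentence in those sections with SAP 8.f and Protocol 10.5.3.
- Reconcile the fever text with the population definition. Protocol 7.4.1 and 8.2.8 remove febrile subjects from the per protocol population without separating its two parts, whereas Protocol 10.4 defines the primary PK part by the first three doses and the Visit 6 sample. Until this is settled, it is unclear whether a subject febrile on Day 28 would be recovered.

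The cost is wording in both documents and one extra model run, with no new data. The downside is that the analysis set is no longer identical at every timepoint; the N columns already in the example table would show this.

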10.5.3. Secondary PK Analysis

Secondary efficacy analyses 2 and 5 will be based on the secondary PK population.

Secondary efficacy analyses 1, 3, and 4 will be based on the primary PK population, since timepoints post-Visit 6 are not included in these analyses.

The secondary PK endpoints will be analyzed as follow:

- 1) the assessment AUC_{0-7d} for BPL HRIG and vaccine versus comparator HRIG and vaccine using a non-inferiority margin of 20%.
- 2) the geometric mean titers (GMTs) for RVNA titer up to peak serum level after administration of BPL HRIG and vaccine or comparator HRIG and vaccine will be assessed using a mixed model repeated measure [MMRM] analysis.
- 3) the proportion of subjects reaching anti-rabies antibody titer of ≥ 0.5 IU/mL at Visits 3-6 after administration of BPL HRIG and vaccine versus comparator HRIG and vaccine will be assessed using a generalized estimated equation [GEE] for a repeated measure analysis.
- 4) the proportion of subjects reaching anti-rabies antibody titer of \geq the lower limit of quantification (LLOQ) of the assay at Visit 3-6 after administration of BPL HRIG and

vaccine versus comparator HRIG and vaccine will be assessed using a generalized estimating equation [GEE] for a repeated measure analysis.

- 5) the GMTs for anti-rabies antibody titer at Visits 6-9 will be compared between treatment groups. Descriptive statistics and visual inspections will be reported as appropriate. No formal hypothesis testing will be performed.

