4. STUDY DESIGN

This will be a prospective, randomized, double-blind, parallel-group, non-inferiority, phase II/III study of the safety and effectiveness of simulated post-exposure prophylaxis with BPL HRIG with co-administration of active rabies vaccine in healthy subjects. This is intended to be a multi-center study. Treatment assignment is blinded until post database lock.

Subjects will be randomized 1:1 to one of the 2 treatment groups, as follows:

HRIG treatment	Rabies vaccine treatment	# of Subjects
BPL HRIG	active rabies vaccine	81
comparator HRIG	active rabies vaccine	81

Prior to randomizing a participant, all screening and baseline evaluations must be completed and the participant determined to be eligible for inclusion in the study. Randomization and the baseline visit (Day 0) should occur no later than 28 days after the completion of the screening visit.

All medicinal product preparation will be performed by the site pharmacist using aseptic techniques and according to a standardized procedure on Day 0, and administration of HRIGs + vaccine will be administered an unblinded nurse administrator. All study assessments and Post Day 0 treatment administration will be performed by blinded study personnel. Investigators and subjects will be blinded to treatment assignment.

Subjects will be identified by a unique five-digit number as follows: each site will be allocated a two-digit site number (e.g. Site 01, etc) and each subject will be allocated a three-digit subject number (e.g. 001) at the Screening Visit. Each subject will be identified by the unique site and subject number combination (e.g. 01001).

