1. a one-sided t-test will be used to assess non-inferiority of the mean of the AUC_{0-7d} of the BPL HRIG + vaccine group to the comparator HRIG + vaccine group. The pre-specified non-inferiority margin is 20%. It will be concluded the mean AUC_{0-7d} in the BPL HRIG + vaccine group is non-inferior to that in the comparator group if the lower limit of the 95% confidence interval for the mean AUC_{0-7d} is greater than -20% of comparator mean AUC_{0-7d}. Log-transformation of the AUC_{0-7d} data will be performed as necessary during statistical testing to meet assumptions for normality.

The null hypothesis is $(\mu_T - \mu_C) / \mu_T \leq -0.2$;

The alternative hypothesis is $(\mu_T - \mu_C) / \mu_T > -0.2$;

Where μ_T =the geometric mean of the AUC_{0-7d} in the BPL HRIG + vaccine group,

μ_C =the geometric mean of the AUC_{0-7d} in the comparator HRIG + vaccine group.

2. The geometric mean titers (GMTs) for RVNA titer up to peak serum level after administration of BPL HRIG and vaccine versus comparator HRIG and vaccine. Due to the observed change in relationship between time and titer level, only PK timepoints up to peak serum level will be included in this analysis.

A generalized estimating equation [GEE] for a repeated measures analysis will be used to assess the difference in proportions between the treatment groups for the third and fourth secondary efficacy analyses. Standard model building methods, diagnostics, and goodness-of-fit measures will be performed as appropriate. Proportions of subjects reaching set anti-rabies antibody titer will be compared at each timepoint as well as throughout all timepoints.

3. The proportion of subjects reaching anti-rabies antibody titer of ≥ 0.5 IU/mL at Visits 3-6 after administration of BPL HRIG and vaccine versus comparator HRIG and vaccine.
4. The proportion of subjects reaching anti-rabies antibody titer of \geq the lower limit of quantitation of the assay at Visit 3-6 after administration of BPL HRIG and vaccine versus comparator HRIG and vaccine. This titer threshold corresponds to the lower limit of quantitation of the assay.

The GEE analysis will include timepoints through Visit 6 for endpoints 3 and 4, at which point all or nearly all subjects are expected to have reached the stated thresholds. There is no clinical benefit of including subsequent timepoints in this analysis.

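### AUC0-7d non-inferiority: the SAP states a 20% margin, but its hypotheses test 16.7%, its decision sentence uses another bound, and the analysis scale is left open

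*SAP*

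**What the plan says.** SAP section 8.f, item 1, contains four statements about the AUC0-7d test:

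- **Margin.** "The pre-specified non-inferiority margin is 20" per cent. SAP section 6 and Protocol sections 8.1.2 and 10.5.3 give the same figure. The protocol wording is "versus comparator HRIG and vaccine using a non-inferiority margin of 20" per cent, with no reference mean, formula or scale.
- **Hypotheses.** H0 is (μT − μC)/μT ≤ −0.2 and H1 is the same expression > −0.2. μT and μC are defined as the geometric means of AUC0-7d in the BPL and comparator groups.
- **Decision sentence.** Non-inferiority is concluded "if the lower limit of the 95% confidence interval for the mean" AUC0-7d "is greater than -20% of comparator mean" AUC0-7d.
- **Scale.** Log-transformation "will be performed as necessary during statistical testing to meet assumptions for normality".

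The test is a one-sided t-test. For the significance level, SAP section 7.a says: "The secondary efficacy endpoint analyses will be considered statistically significant using a two-sided significance level of 0.05".

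**The concern.** These statements do not define one test. The hypotheses scale the difference by the BPL mean and the decision sentence by the comparator mean, so they set different bounds. The decision sentence also names an interval for a mean rather than for a difference or ratio. The hypotheses concern geometric means, yet the log scale on which such means are compared is used only if the data seem to need it.

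AUC0-7d is the only secondary endpoint with a non-inferiority margin. Protocol section 2.9 chooses it to compare the HRIGs before vaccine-induced antibody appears. Titers on Days 3, 5 and 7 describe the same period but carry no margin. If the printed hypotheses govern, BPL can fail a test that it would pass at the stated 20%. If the decision sentence governs, a reader can object that the printed null was not rejected.

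**Working it through.** **Step 1. Does the stated 20% follow from the text?**

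- *Hypotheses.* (μT − μC)/μT = 1 − μC/μT. Setting this above −0.2 gives μC/μT < 1.2, so μT/μC > 1/1.2 = 0.833. The margin against the comparator is 1 − 0.833 = 16.7%. The 20% is not reproduced. In this algebraic form a true 20% margin would be (0.80 − 1)/0.80 = −0.25.
- *Decision sentence, read as an interval for the difference.* μT − μC > −0.2 μC gives μT/μC > 0.80. The 20% is reproduced.
- *Decision sentence, read literally.* An interval for a mean AUC, a positive quantity, is compared with a negative number. On the raw scale this is essentially always met, so it is almost certainly not what was meant.

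**Step 2. What the two bounds mean in practice**

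Inputs: 73 evaluable subjects per arm (Protocol section 10.9, where the figure is derived for the primary endpoint) and a two-sided 95% interval (SAP section 7.a). Assumptions: log-normal AUC0-7d, and CV of 30, 40 or 50%, because the documents give no CV.

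- SE of the log ratio = √ln(1 + CV²) × √(2/73)
- Power = Φ[(ln R − ln bound)/SE − 1.96], where R is the true ratio
- Lowest observed ratio that passes = bound × exp(1.977 × SE), with 1.977 the t quantile on 144 df
- False-claim rate at R = 0.80 with the 0.833 bound: noncentral t

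The log margins are −ln 0.80 = 0.2231 and −ln 0.8333 = 0.1823. At CV 40% and R = 1, power is Φ(0.2231/0.0638 − 1.96) = 93.8% for bound 0.80 and Φ(0.1823/0.0638 − 1.96) = 81.6% for bound 0.833.

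Paired entries show bound 0.80, then bound 0.833.

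| CV | SE | Power, R = 1.0 | Power, R = 0.95 | Lowest passing ratio | False claims at R = 0.80, bound 0.833 |
|---|---|---|---|---|---|
| 30% | 0.0486 | 99.6% / 96.3% | 94.3% / 76.9% | 0.881 / 0.917 | 0.3% |
| 40% | 0.0638 | 93.8% / 81.6% | 76.9% / 53.8% | 0.907 / 0.945 | 0.5% |
| 50% | 0.0782 | 81.4% / 64.5% | 59.4% / 38.8% | 0.934 / 0.973 | 0.7% |

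Any trial that passes at 0.833 also passes at 0.80, so the difference in power is the chance of conflicting verdicts. At R = 1.0 it is 3.3, 12.2 and 16.9 percentage points. At R = 0.95 it is 17.4, 23.1 and 20.6 points.

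Matching the 0.80-bound power at R = 1.0 under the 0.833 bound needs (0.2231/0.1823)² = 1.498 times the subjects, or 73 × 1.498 = 109.3, about 110 per arm.

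**Step 3. Effect of the open scale**

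In 100,000 simulated trials per CV, with equal CV in both arms, the raw-scale rule required the lower 95% limit for the difference in arithmetic means to exceed −0.2 times the comparator mean. Power at R = 1.0 was 98.7/87.8/69.3%, against 99.5/93.7/80.9% on the log scale at bound 0.80. The raw rule's false-claim rate at R = 0.80 was about 1.5%.

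Equal CVs make the arithmetic and geometric ratios equal, so the simulation shows only a loss of power. If the CVs differ, the two scales estimate different ratios: arithmetic ratio = geometric ratio × √[(1 + CV_T²)/(1 + CV_C²)]. With CV 50% for BPL and 30% for the comparator the factor is √(1.25/1.09) = 1.071, so a geometric ratio of 0.80 is an arithmetic ratio of 0.857.

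**The case against.** The strongest reply is that 20% is stated repeatedly and that the decision sentence, which says when non-inferiority is concluded, refers to the comparator mean. On that view the denominator is a wrong subscript, the intended bound is 0.80, and the power figures at 0.833 price a test nobody planned. This is a plausible reading of intent. It does not settle the matter, because the same denominator stands in both hypotheses and the decision sentence is itself misworded. A misread subscript in the extracted text is possible but unlikely, since both lines agree and the numerator distinguishes the groups.

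Second, defining μT and μC as geometric means arguably fixes the target, with the transformation clause concerning only normality. That narrows the ambiguity, but a geometric-mean hypothesis tested with untransformed data is still a mismatch.

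Third, the literal decision rule is not met in every conceivable case, since a mean of ln(AUC0-7d) can be negative. That is correct, which is why step 1 confines the statement to the raw scale.

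Fourth, the figures rest on assumptions. No CV or power for AUC0-7d is given, and the primary PK population requires the Visit 6 sample but not those of Days 3, 5 and 7, so 73 per arm may not be the number analysed. The power formula is a normal approximation; noncentral t gives 99.5/93.5/80.9% and 96.1/81.1/63.9% at R = 1.0, within about 0.6 points. These points affect the illustration, not the algebra.

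**Conclusion.** The concern holds. The stated margin (20%), the hypotheses (16.7%) and the decision sentence (20% only if read as a difference) disagree, and neither the protocol nor the rest of the SAP resolves this. The algebra needs no assumption.

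The practical size depends on the unknown variability. Across the assumed CVs of 30 to 50%, the stricter bound costs about 3 to 17 points of power for a product equal to the comparator and about 17 to 23 points at a true ratio of 0.95.

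The error in the hypotheses is conservative: at a true ratio of 0.80 they would give a false claim in 0.3 to 0.7% of trials rather than 2.5%. It concerns one secondary endpoint and leaves the primary Day 14 analysis alone. It should be fixed because a result between the bounds would have no agreed interpretation.

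**What to change.** Replace item 1 of SAP section 8.f before database lock and unblinding with text such as:

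> H0: μT/μC ≤ 0.80 versus H1: μT/μC > 0.80, where μT and μC are the geometric means of AUC0-7d in the BPL and comparator groups. ln(AUC0-7d) will be analysed in all cases. Non-inferiority is concluded if the lower limit of the two-sided 95% confidence interval for the BPL/comparator geometric mean ratio exceeds 0.80.

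Delete the conditional transformation clause and the bound expressed as a percentage of the comparator mean. The two-sided 95% interval agrees with the level in SAP section 7.a.

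Moving from the printed 0.833 to 0.80 makes the test easier for BPL, so the reason should be recorded while the study is blinded. SAP section 4 allows for this: "Treatment assignment is blinded until post database lock". If 0.833 was intended, keep it and state a 16.7% margin in both the SAP and the protocol.

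The cost is SAP wording only, plus the protocol margin wording if 0.833 is kept. Data collection and sample size do not change.
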